7.8 Concomitant medications/treatments

For any treatment other than the IMP, including over-the-counter products, an accurate record must be kept in the source documents and in the eCRF.

All concomitant medications should be recorded in the eCRF at the EV and subsequently be recorded only if there is a change regarding the administration of the medication. For all subjects, new medications should be recorded in the eCRF at only the first visit at which they are reported and subsequently only if there is a change. For any change, the start date corresponding to the date of change in administration should be recorded in the eCRF.

For all subjects, all changes in concomitant AEDs and non-AEDs will be recorded on the AED or non-AED concomitant medication page, respectively, in the eCRF. This record should include the name of the drug (preferably the brand name), the dose, the date(s) of administration, formulation(s), and the indication for use.

7.8.1 Permitted concomitant treatments (medications and therapies)

At the beginning of EP0085, the concomitant AEDs that were used in EP0083 and N01379 are permitted for rollover subjects. Subjects directly enrolled into EP0085 in Japan will enter the study receiving at least 1 permitted concomitant AED.

The investigator (or designee) will be allowed to change the type, dosage and administration, or discontinuation/resumption of concomitant AEDs to optimize tolerability and seizure reduction for each subject. Antiepileptic drugs (Appendix 3 [Section 16.3]) are permitted during the study. Changes in concomitant AEDs will be allowed only if the dose of BRV has been stable for the previous 4 weeks; BRV dose must remain stable during changes to concomitant AEDs. New AEDs may be added only when the subject has not optimally or adequately responded to a maximum tolerated dose of BRV. The concomitant AEDs can be carefully tapered or discontinued at the discretion of the investigator.

Monotherapy with BRV is permitted. Increasing the dose of BRV and/or concomitant AEDs, as well as addition of a new AED should be done at a visit (scheduled or unscheduled). There are no restrictions for concomitant AEDs during the Taper Period, considering subject safety.

Vagal nerve stimulation (VNS) is allowed and will be counted as a concomitant AED.

7.8.2 Prohibited concomitant treatments (medications and therapies)

The following concomitant medications/treatments are prohibited during the study:

- BRV (other than IMP)
- LEV (LEV is not prohibited for directly enrolled subjects in Japan)
- Potassium bromide, sodium bromide, and calcium bromide
- Other investigational products and drugs and medical devices that have not been approved in each country
- Brain surgery (including surgery for examination purposes).

7.8.3 Rescue medication

The rescue medication(s) which the dosage form is suppository, injection, and enema preparation are permitted during the study for sudden aggravation or cluster seizures, and if the subject's condition requires rescue medication(s) during minor surgical procedures in a relatively short time. The use of rescue medication is permitted only once a week for a maximum of 4 weeks to control seizures; if the frequency exceeds once a week, the subject will be discontinued from the study.

7.9 Blinding

This is an open-label LTFU study of the preceding double-blind study EP0083 and open-label study N01379, thus, subjects are not blinded.

7.10 Randomization and numbering of subjects

Since EP0085 is an open-label LTFU study for EP0083 and open-label study N01379, subjects will not be randomized to any treatment groups. Subjects from EP0083 will start with a dose of BRV 100mg/day (2 equally divided doses administered twice daily) and will be maintained on that dose for at least 2 weeks, unless they are unable to tolerate the dose. Subjects from Japan who participated in N01379 can enter EP0085 at a dose up to 200mg/day.

Subjects from EP0083 and N01379 will continue with the 5-digit subject numbers assigned by the IVRS/IWRS in the preceding studies. Directly enrolled subjects will receive a 5-digit number assigned by the IVRS/IWRS at Screening that serves as the subject identifier throughout the study.

8 STUDY PROCEDURES BY VISIT

Prior to any study activities, the subject/parent(s)/legal representative(s) will be asked to read and sign an ICF that has been approved by an IRB/IEC and which complies with regulatory requirements. The subject/parent(s)/legal representative(s) will be given adequate time to consider any information concerning the study, given to them by the Investigator or designee. As part of the informed consent procedure, the subject/parent(s) or legal representative(s) will be given the opportunity to ask the Investigator any questions regarding potential risks and benefits of participation in the study. Additionally, if applicable (according to subject's age and local requirements), the subject will sign an IRB/IEC-approved Assent form.

8.1 Screening Visit (for direct enrollers in Japan only)

The following tasks and procedures are to be performed between Day -21 and Day -2, prior to Visit 1 (EV) for direct enrollers in Japan:

- Written informed consent
- Subject identification card dispensed
- Eligibility assessment
- Demography
- Medical/procedures history
- Epilepsy history
- AED history
- Birth control
- Vital signs
- Body weight
- Height
- Physical examination
- Neurological examination
- 12-lead ECG
- EEG (if no EEG result within the previous 10 years is available)
- Neuro-imaging procedure (per Investigator discretion)
- IVRS/IWRS
- Seizure counts (prospectively recorded historical seizure information)
- Laboratory safety assessments including hematology, blood chemistry, and urinalysis
- Serum pregnancy test
- AE reporting
- C-SSRS
- Medical procedures
- Concomitant AEDs
- Concomitant non-AEDs

8.2 Entry Visit (for direct enrollers in Japan only)

The EV assessments for direct enrollers in Japan are as follows:

- Eligibility assessment
- Vital signs
- Body weight
- IVRS/IWRS

- Subject's daily record card (DRC) dispensed
- Seizure counts (prospectively recorded historical seizure information)
- Laboratory safety assessments including hematology, blood chemistry, urinalysis and urine pregnancy test (if applicable)
- AE reporting
- C-SSRS
- Medical procedures
- Concomitant AEDs
- Concomitant non-AEDs
- Study drug dispensing

8.3 Entry Visit (rollovers from China and Japan)

The following tasks and procedures are to be performed at this visit (for subjects who have completed EP0083 and N01379, assessments marked [*] should have already been completed during the last visit of the previous protocol and do not need to be repeated at Visit 1).

The EV assessments are as follows:

- Written informed consent (must be obtained during the previous study)
- Subject identification card dispensed
- Eligibility assessment
- Demography
- Vital signs*
- Body weight*
- Height
- Physical examination*
- Neurological examination*
- 12-lead ECG*
- IVRS/IWRS
- Subject's daily record card (DRC) dispensed
- Seizure counts*
- Laboratory safety assessments including hematology, blood chemistry, urinalysis and urine pregnancy test (if applicable)*
- AE reporting*
 - Ongoing AEs at the time of subject completion of EP0083 or N01379 will be obtained from the database for EP0083 or N01379 and should not be recorded on the eCRF for

EP0085, unless there is a change in intensity or seriousness. In this event, the AE should be recorded on the eCRF for EP0085 with the onset date corresponding to the date of change in condition.

- C-SSRS*
- Medical procedures*
- Concomitant AEDs*
 - Ongoing medications (AEDs and non-AEDs) at the time of subject completion of EP0083 or N01379 will be obtained from the database for EP0083 or N01379 and should not be recorded on the eCRF for EP0085, unless there is a change regarding the administration of the medication. In this event, the medication should be recorded on the eCRF for EP0085 with the start date corresponding to the date of change in administration.
- Concomitant non-AEDs*
- Study drug dispensing

The following data will be obtained from the Baseline of EP0083 or N01358 (for subjects entering from N01379) and do not need to be recorded on the eCRF for this study.

- General medical and procedures history
- AED history
- Epilepsy history.

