At selected sites in Japan, Japanese subjects may participate in an additional study (EP0118) with the intravenous formulation of BRV without withdrawing from EP0085. Ten evaluable subjects are planned for EP0118, and the total duration in the study for each subject is 7 days. The study period of EP0118 will be included in that of EP0085. Subjects will continue to receive their current dose of BRV at the time of entry and it will remain stable for the duration of EP0118. Subjects who complete or withdraw from EP0118 will resume their participation in EP0085 with oral BRV treatment. In the event that a subject withdraws from EP0118 and is required to down-titrate BRV treatment, the subject will return to EP0085 and down-titrate using BRV tablets. Treatment-emergent AEs and concomitant treatment(s)/medication(s) that occur or are administered during EP0118 will be recorded in EP0118. Ongoing TEAEs and concomitant medication(s)/medical procedure(s) originating from EP0118 will be recorded and followed in EP0085 until resolution or until the status of the TEAE and/or concomitant medications are stable. All other data reported for EP0118 will be captured in the EP0118 database. Per the EP0118 protocol, the study (EP0118) will require hospitalization. Hospitalization for study participation does not need to be reported as an SAE.

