12.8 Determination of sample size

For this open-label LTFU study, no sample size calculation will be performed. The sample size will depend upon recruitment into and completion of the previous study. Overall, approximately 217 subjects are planned for enrollment. In Japan, it is estimated that approximately 127 subjects will enter the study. This estimate assumes that at least 90% of randomized Japanese subjects will complete EP0083 (approximately 90 subjects) or enroll from N01379 sites in Japan (7 subjects) and the plan that 30 Japanese subjects will be directly enrolled in this study. Likewise, at least 90% of randomized Chinese subjects will be assumed to complete EP0083 (approximately 90 subjects).

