## 3 DATA ANALYSIS CONSIDERATIONS

### 3.1 General presentation of summaries and analyses

For the analysis purposes, “core study” in this plan refers to the study where the subjects were firstly enrolled. For rollover subjects, the core study is N01358 (for rollover subjects from N01379) or EP0083 (for rollover subjects from EP0083). For direct enrollers EP0085 is the core study.

Statistical analysis and generation of tables, figures, subject data listings, and statistical output will be performed using SAS® Version 9.3 or higher.

Descriptive statistics will be displayed to provide an overview of the study results. For categorical parameters, the number and percentage of subjects in each category will be presented. The denominator for percentages will be based on the number of subjects appropriate for the purpose of analysis. Unless otherwise noted, all percentages will be displayed to 1 decimal place. No percentage will be displayed for zero counts, and no decimal will be presented when the percentage is 100%.

For continuous parameters, descriptive statistics will include number of subjects with available measurements (n), mean, standard deviation (SD), median, minimum, and maximum. Decimal places for descriptive statistics will always apply the following rules:

- “n” will be an integer.
- Mean, SD and median will use 1 additional decimal place compared to the original data.
- Minimum and maximum will have the same number of decimal places as the original value.

All summaries will be descriptive; no statistical hypothesis testing is planned.

Subject data listings will be provided and will present source data and key derived variables for statistical analyses.

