## **4 STATISTICAL/ANALYTICAL ISSUES**

### **4.1 Handling of missing data**

No rule for handling of missing data will be applied for this LTFU study. Safety and efficacy variables will be analyzed as available. Days with missing information will be ignored in the calculation of the seizure frequency.

Since subjects may drop out from the study at different times, selected summaries will be presented by time interval.

Subjects participating in EP0118 while also enrolled in EP0085 will have missing data for seizure frequency and drug dosing while participating in the EP0118 study. As the duration of the EP0118 study will be short (3-7 days), no imputation for data missing due to participation in EP0118 will be performed. Subjects will be assigned the same dose in EP0118 as that assigned in EP0085 for the two weeks prior to the start of EP0118. As such, time during the EP0118 study will not be subtracted from the exposure calculations (eg, exposure will be from the start of BRV treatment in the EP0085 study until the date of last dose of BRV in EP0085).

For the calculation of variables related to seizure frequency, the dates during participation in EP0118 will be considered as not done for the purpose of efficacy analyses for EP0085 according to the Seizure Count form entry (eg, these dates will not be considered as days evaluated for seizure frequency).

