## **9.2 Primary safety variables**

### **9.2.1 Definition of treatment-emergent adverse events**

AEs will be classified as either pre-treatment or treatment-emergent. Pre-treatment AEs are defined as AEs which had onset prior to the date of the first dose of BRV in EP0085 study. Treatment-emergent AEs (TEAEs) are defined as AEs that had onset on or after the day of first BRV dose in EP0085 study. AEs with an incomplete onset date will be classified as TEAEs if the month and year of onset (when only the month and year are specified) is the same as the month and year of the first BRV dose or the year of onset (when only year is specified) is the same as the year of first BRV dose.

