### **9.2.2.2 Withdrawal due to adverse events**

All TEAEs collected with a study drug action taken as “Drug permanently withdrawn” will be summarized in a table by SOC and PT in a manner similar to that described in the Section 9.2.2.1. All AE leading to study discontinuation or permanently withdrawal of study drug will be listed by subject.

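### An unchanged adverse event carried over from EP0083 or N01379 that leads to brivaracetam being reduced, interrupted or stopped is absent from the EP0085 withdrawal and dose-change tables

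*Protocol*

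**What the plan says.** For rollover subjects, Protocol 8.3 takes AEs ongoing at the end of the feeder study from that study's database. They are kept off the form used in "EP0085, unless there is a change in intensity or seriousness. In this event, the AE should be recorded on the eCRF for EP0085". Such an entry takes the date of the change as its new onset date. The general collection rule (Protocol 10.1.1.1) names AEs that are new, recurrent or worse, and the repetition rule (Protocol 10.1.2.2) applies when intensity increases.

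In SAP 9.2.1, TEAEs "are defined as AEs that had onset on or after the day of first BRV dose in EP0085 study". AEs with earlier onset are listed but not summarised (SAP 9.2.2). The withdrawal table covers "All TEAEs collected with a study drug action taken as" permanent withdrawal. The dose-change table in SAP 9.2.2.7 is built the same way for reductions, increases and temporary interruptions.

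For the intravenous sub-study EP0118, Protocol 5.1.1 says that treatment-emergent AEs "that occur or are administered during EP0118 will be recorded in EP0118", while those still ongoing afterwards pass to EP0085. SAP 4.1 adds that "time during the EP0118 study will not be subtracted from the exposure calculations".

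**The concern.** The primary objective is long-term safety and tolerability. BRV dose is flexible and is adjusted partly for tolerability, so AEs that lead to a lower dose, an interruption or a stop are central results. A side effect that persists without worsening is a plausible reason for such an action.

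Both recording triggers concern the AE itself, and neither concerns what is done with BRV because of it. In the same section, an ongoing medication does return to the EP0085 form when its administration changes. AEs have no corresponding rule for a change in BRV. Because the two action tables are restricted to TEAEs, the recording gap becomes a reporting gap: the action happens in EP0085, but the AE behind it has no row in the table meant to show it.

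**Working it through.** The plan offers no test or power figure to check: "All summaries will be descriptive; no statistical hypothesis testing is planned". The check consists of the planned counts, a trace of each case through the rules, and a bound.

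**1. Planned counts (Protocol 12.8).** "Overall, approximately 217 subjects are planned for enrollment", and "In Japan, it is estimated that approximately 127 subjects will enter the study". The components are 90 from EP0083 in Japan, 7 from N01379, 30 direct enrollers and 90 from EP0083 in China.
- Japan: 90 + 7 + 30 = 127
- Total: 127 + 90 = 217

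Both stated figures reproduce.

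**2. Subjects under the carry-over rule.** 90 + 7 + 90 = 187, and 187/217 = 86.2%. This counts subjects to whom the rule applies, not subjects with an ongoing AE.

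**3. Tracing a carried-over AE.**
- *Intensity or seriousness changes.* The AE is recorded in EP0085 with the date of change as onset. If that date is on or after the first EP0085 dose, it is a TEAE and any BRV action is counted. There is no gap.
- *Unchanged, and BRV is stopped.* There is no EP0085 AE record, onset lies in the feeder study, and the AE is not a TEAE, so it is absent from the SAP 9.2.2.2 table. The stop is still counted in three places: the primary reason for withdrawal on the eCRF (Protocol 6.3), the table of subjects who discontinued because of an AE (SAP 5.1), and the all-cause time-to-discontinuation analysis (SAP 5.4).
- *Unchanged, and BRV dose is changed or interrupted without a stop.* The AE is absent from the SAP 9.2.2.7 table. No disposition record exists. Dosing is listed (SAP 7), but the documents do not say that the listing carries the reason.

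**4. Cause-specific discontinuation (SAP 5.4).** The analysis of stops due to a TEAE does not say whether the cause comes from the AE page or the termination page. Whether a stop for a carried-over AE counts as an event there cannot be determined.

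**5. Size.** The documents do not give the number affected, k. Taking the Safety Set as the planned enrolment, the understatement in the All Subjects column is 100 × k/217 points. Over an assumed range for k:
- k = 0: 0
- k = 1: 0.46
- k = 5: 2.3
- k = 10: 4.6

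In the N01379 column (n = 7), one subject is 100 × 1/7 = 14.3 points.

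**6. EP0118.** 10 subjects × 7 days = 70 subject-days, and 70/365.25 = 0.19 subject-years. Only AEs that both start and resolve inside that window stay outside the EP0085 data. TEAE percentages use Safety Set subjects as denominator (SAP 9.2.2.1), and the current SAP plans no exposure-adjusted AE rate, so keeping those days in exposure distorts no planned incidence figure.

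**The case against.** The strongest reply is that stops do not depend on a TEAE record. The withdrawal reason, disposition by AE and all-cause discontinuation all capture them, and the SAP 9.2.2.2 listing covers all AEs leading to discontinuation, not only TEAEs. The first three stand for stops. They need not identify the event by system organ class and preferred term, though, and the listing needs an AE record that carries the BRV action. EP0085 holds none in this case, and neither document says that the feeder record is updated with an action taken later.

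A second reply is that onset-based TEAEs, with feeder events not re-entered, prevent double counting. That is sound. It argues against counting carried-over AEs inside the TEAE tables, but not against recording them when they cause a BRV action.

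Third, the eCRF completion guidelines and the feeder studies' follow-up rules are not available and might fill the gap. Nothing in the protocol or SAP says so. Rollovers must also be judged likely to benefit from long-term BRV, which may make persistent troublesome AEs at entry less common. For both reasons the size must stay open.

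A reader might also infer that the rule makes the study-group columns non-comparable because direct enrollers have no feeder study. The documents do not support this. SAP 9.2.1 applies one onset rule to everyone, so a direct enroller's unchanged AE from before the first dose is also absent from both TEAE tables. The difference lies in recording: that AE is at least on the EP0085 form.

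**Conclusion.** The gap is real and narrow. If the plan is followed exactly, an unchanged feeder-study AE that leads to a BRV action in EP0085 is left out of the AE-attributed withdrawal and dose-change tables. The case is clearest for dose changes and interruptions without a stop, which have no other summary. The rule applies to 187 of 217 planned subjects; each affected subject is 0.46 points of All Subjects. This rests on planned rather than actual enrolment and on the two documents alone; the number affected is unknown and may be zero.

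Two stronger readings should be resisted. A reader might infer that tolerability results as a whole are understated. They are not shown to be, because AEs that change are recorded and stops are counted elsewhere. A reader might also infer that EP0118 opens a material hole in the safety data. It involves about 10 subjects and 0.19 subject-years, its ongoing AEs do pass to EP0085, and it feeds no exposure-adjusted rate.

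**What to change.** - **Protocol 8.3:** add a third trigger. A carried-over AE is also recorded in EP0085 when it leads to any action taken with BRV there. Keep the original onset date and record the date of the action.
- **SAP 9.2.2.2 and 9.2.2.7:** leave the TEAE tables as defined. Add a separate row or supplementary summary of all AEs, including carried-over ones, that lead to BRV withdrawal or dose change in EP0085. Placing these AEs inside the TEAE tables would contradict SAP 9.2.1.
- **SAP 5.4:** state that the AE cause of discontinuation includes carried-over AEs, and whether it is read from the AE page or the termination page.
- **EP0118:** at most, a separate listing of its AEs for EP0085 subjects. Pooling would mix events from an intravenous period into tables for an oral-tablet study.

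The cost is one protocol sentence, a small change to the eCRF completion guideline and some SAP wording. The new summary may show slightly higher AE withdrawal and dose-change percentages than the TEAE tables. Only data capture and reporting change; treatment does not.

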7.2 Treatments to be administered

Directly enrolled subjects in Japan and subjects rolling over from EP0083 will be started on a BRV dose of 100mg/day (2 equally divided doses administered twice daily) at study entry and should be maintained at this dose for at least 2 weeks, unless the subject is not able to tolerate treatment.

Subjects from Japan who entered from N01379 can enter EP0085 at a dose up to 200mg/day. The BRV dose can be adjusted based on the individual subject's seizure control and tolerability between 50mg/day and 200mg/day during the study and must always be administered in equal morning and evening doses except the last week of down-titration. Of note, decreasing the dose should not exceed 50mg/day.

For all subjects, the first intake of study medication should occur in the evening of the day of the EV. Subjects should take tablets according to instructions provided by the Investigator.

During the Down-Titration Period, the BRV dose may be decreased in steps of a maximum of 50mg/day on a weekly basis. A last down-titration step at 25mg/day for 1 week should be included prior to the 2-week Study Drug-Free Period. The subject will be required to enter a 2-week Study Drug-Free Period for 2 weeks, followed by a FV.

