10 ASSESSMENT OF SAFETY

10.1 Adverse events

10.1.1 Definitions

10.1.1.1 Adverse event

An AE is any untoward medical occurrence in a patient or clinical investigation subject administered a pharmaceutical product that does not necessarily have a causal relationship with this treatment. An AE can therefore be any unfavorable and unintended sign (including an abnormal laboratory finding), symptom, or disease temporally associated with the use of a medicinal (investigational) product, whether or not related to the medicinal (investigational) product.

In order to ensure complete safety data collection, all AEs occurring during the study (ie, after the signing of the ICF), including any pretreatment and posttreatment periods required by the protocol, must be reported in the eCRF even if no IMP was taken but specific study procedures were conducted. This includes all AEs not present prior to the initial visit and all AEs that recurred or worsened after the initial visit.

Signs or symptoms of the condition/disease for which the IMP is being studied should be recorded as AEs only if their nature changes considerably or their frequency or intensity increases in a clinically significant manner as compared to the clinical profile known to the Investigator from the subject's history or the Baseline Period.

For results disclosure on public registries (eg, ClinicalTrials.gov), TEAEs and treatment-emergent SAEs will be published.

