10.1.2.2 Rule for repetition of an AE

An increase in the intensity of an AE should lead to the repetition of the AE being reported with:

- The outcome date of the first AE that is not related to the natural course of the disease being the same as the start date of the repeated AE, and the outcome of “worsening”
- The AE verbatim term being the same for the first and repeated AE, so that the repeated AE can be easily identified as the worsening of the first one

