### 3.2 Analysis time points

#### 3.2.1 First and last dose of BRV

Unless otherwise noted, all references to the first dose of BRV in this SAP refer to the first dose of BRV during EP0085 (ie, not the first dose of BRV from the previous study in which subjects participated in prior to EP0085). Unless otherwise noted, all references to the last

known dose of BRV in this SAP refer to the last dose of BRV taken across any study periods (ie, the last dose of BRV across both the Evaluation and Down-Titration Periods).

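### Protocol 8.3 re-dates a carried-over AE on any change, so with TEAEs defined by onset date alone an improving AE in a rollover subject counts as a new TEAE

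*Protocol*

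**What the plan says.** **Recording rule for rollovers.** Under Protocol 8.3, an AE ongoing when the subject completes EP0083 or N01379 is taken from that study's database. It is not entered again in EP0085 "unless there is a change in intensity or seriousness. In this event, the AE should be recorded on the eCRF for EP0085". The same sentence dates this new record from the change, not from the original start: "with the onset date corresponding to the date of change in condition". The text does not say whether the change must be for the worse.

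**General AE rules.** Protocol 10.1.1.1 requires all AEs during the study to be reported and says that this includes "all AEs that recurred or worsened after the initial visit". Protocol 10.1.2.2 covers repeated records: "An increase in the intensity of an AE should lead to the repetition of the AE being reported with" the stop date of the first record as the start date of the second, the same verbatim term, and an outcome that denotes worsening. Neither section refers to 8.3.

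**Analysis rule.** SAP 9.2.1: "Treatment-emergent AEs (TEAEs) are defined as AEs that had onset on or after the day of first BRV dose in EP0085 study". SAP 3.2.1 fixes the reference point: "all references to the first dose of BRV in this SAP refer to the first dose of BRV during EP0085". SAP 9.2.2 assigns TEAEs to study periods and 3-month intervals by onset date. Neither 9.2.2 nor 9.2.2.1 sets a rule for carried-over events. TEAEs are the primary safety variable (Protocol 4.1.1, SAP 2.2.1.1).

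**The concern.** The 8.3 rule has a sound purpose: an AE that began in the feeder study and worsens on EP0085 treatment should be visible in EP0085. As worded, it also catches the opposite course. Severe dizziness carried over from EP0083 that eases to moderate after entry meets the trigger, receives an EP0085 onset date, and passes the onset-date test in the SAP. It would be tabulated as a moderate TEAE although nothing new or worse happened.

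At stake is the meaning of the primary variable. A TEAE table should show events that arose or worsened on treatment, and Protocol 10.1.1.1 commits TEAEs and treatment-emergent SAEs to publication on public registries. If an easing AE keeps its serious flag on the new record, it would also appear in the treatment-emergent SAE tables. The two recording rules also let two sites handle the same clinical course differently, depending on which section they follow.

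**Working it through.** The plan states no figure for this point and there is no sample size or power calculation to reproduce. The check is a chain of rules, followed by the effect of one affected subject.

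**Chain of rules for a carried-over AE that eases**

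1. *Is it re-recorded?* Under 8.3, yes: a fall in intensity is a change in intensity.
2. *With what onset date?* The date of the change, under the same section.
3. *Is that date on or after the first EP0085 dose?* Protocol 7.2 says: "For all subjects, the first intake of study medication should occur in the evening of the day of the EV". SAP 9.2.1 works by calendar day, so a change on the Entry Visit day or later qualifies. A change dated earlier would be pre-treatment.
4. *Does the SAP remove it?* No. Section 9.2.1 has no worsening criterion, and 9.2.2 and 9.2.2.1 add none.

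The same course in a direct enroller, with an AE that starts in EP0085 and then eases, produces no second record under 10.1.2.2, because that rule is triggered by an increase.

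**Who is exposed (planned numbers, Protocol 12.8)**

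- Agreement with the stated totals: Japan 90 + 7 + 30 = 127; overall 127 + 90 = 217.
- Rollovers: 90 + 7 + 90 = 187, and 187/217 = 86.2%.
- Direct enrollers: 30, not exposed.

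**Effect of one subject who is a TEAE case only through an improving carried-over AE**

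| Column | Calculation | Percentage points |
|---|---|---|
| All Subjects | 1/217 | 0.46 |
| EP0083 Total | 1/180 | 0.56 |
| N01379 | 1/7 | 14.3 |

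**Scale under assumed shares.** The documents give neither the share of rollovers who enter with an ongoing AE nor the share whose AE eases. The shares below are assumptions, and the formula is share × 187 / 217.

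| Assumed share of rollovers who are cases only for this reason | Subjects | All Subjects, percentage points |
|---|---|---|
| 1% | 1.87 | 0.86 |
| 2% | 3.74 | 1.72 |
| 5% | 9.35 | 4.31 |
| 10% | 18.7 | 8.62 |

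For a share defined more loosely, as all rollovers with an improving carried-over AE, these are upper bounds on incidence. SAP 9.2.2.1 counts a subject once per SOC or PT, so someone with another TEAE of the same term adds nothing to incidence. The event count still rises by one per record.

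**The case against.** **The protocol already points to worsening.** Sections 10.1.1.1 and 10.1.2.2 suggest that worsening was intended, and sites may read 8.3 that way. The eCRF Completion Guidelines, which Protocol 10.1.2.1 cites for AE entry, are not among the documents. This stands in part: it limits what can be said about practice, but it does not alter what 8.3 instructs. A reader might go further and infer that the two general sections restrict re-recording to worsening, in flat contradiction of 8.3. They do not say that. 10.1.1.1 lists what reporting includes, and 10.1.2.2 is silent on decreases. The defect is that the triggers differ and nothing says which prevails.

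**8.3 may apply at the Entry Visit only.** The sentence sits in the Entry Visit list, and the later visit sections do not repeat it. This reading is weak. The rule concerns AEs ongoing at feeder-study completion, and dosing starts that same evening, so it would have little to govern if it lapsed at the end of the visit.

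**An AE does not become non-serious.** Protocol 10.1.1.2 defines seriousness by whether a criterion was met and describes no route back. This stands, so the point rests on intensity.

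**The effect is harmless.** All summaries are descriptive, with no testing (SAP 3.1), and the error overstates harm. A reader might infer that a rollover-versus-direct-enroller comparison is biased. SAP 3.6 has those groups analysed separately and plans no such comparison, so the columns are affected but no planned contrast is. Still, no passage presents over-counting as deliberate caution.

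**An SAP filter could delete genuine recurrences.** A carried-over AE that did not change has no EP0085 record, so its resolution may be missing from the EP0085 data, and a later recurrence could be mistaken for a continuation. This stands and shapes the fix.

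**Conclusion.** The point holds as a wording defect with a defined consequence. Protocol 8.3 and SAP 9.2.1, each applied as written, count an improving carried-over AE as a new TEAE, in rollover subjects only. The conclusion assumes that sites apply 8.3 literally and that the change falls on or after the day of the first EP0085 dose.

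A reader might infer that such records exist in number, that TEAE incidence is inflated by a known amount, or that the excess falls mainly in the first 3-month interval. The documents support none of these: they give no frequency of ongoing AEs at entry, no frequency of improvement, and no timing. What can be stated is the effect per subject: 0.46 points in All Subjects, 0.56 in EP0083 Total and 14.3 in N01379. Only in the 7-subject N01379 group would a single case visibly move a percentage.

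This should be corrected because it touches the primary variable and is cheap to repair. It does not threaten any inference.

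**What to change.** **Protocol 8.3.** Replace the undirected trigger with *an increase in intensity, or the AE becoming serious*. The intensity part follows the worsening principle of 10.1.1.1 and 10.1.2.2. The seriousness part keeps the element that 8.3 already has, in the direction that matters for safety.

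**SAP 9.2.1, for records already collected.** Add a rule along these lines:

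- A re-recorded AE that continues an AE still ongoing at feeder-study completion counts as a TEAE only if, relative to its last record in EP0083 or N01379, it increased in intensity or became serious.
- A recurrence after resolution remains a TEAE.
- A record whose continuity cannot be confirmed remains a TEAE.
- Records excluded under this rule stay in the AE listings.

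The third item guards against losing true events. Matching on term alone is not enough, because 8.3 does not require the same verbatim term and resolution of an unchanged carried-over AE may not be in the EP0085 data.

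**Cost.** One phrase in the protocol, a short SAP rule, and a small matching step against the prior-study AE data, which 8.3 already says will be drawn from those databases. TEAE counts can stay the same or fall. How far they fall cannot be known in advance, but the excluded records remain visible for review.
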